3.2 Exclusion Criteria

1. Known allergy or intolerance to duvelisib or another PI3K inhibitor.
2. Known or suspected active viral (including CMV, HIV, hepatitis B, and hepatitis C), bacterial, mycobacterial, or fungal infection other than COVID-19. CMV viral load will be assessed at screening and those with viremia will be excluded. Other virologic testing not required unless infection is suspected.
3. Pregnant and/or breastfeeding.
4. Any uncontrolled intercurrent illness that would put the patient at greater risk or limit compliance with study requirements in the opinion of the investigator.

3.3 Inclusion of Women and Minorities

Both men and women and members of all races and ethnic groups are eligible for this trial. The study is limited to adults over the age of 18 as the safety of duvelisib in minors has not been established.

4.0 REGISTRATION PROCEDURES

4.1 Confirmation of Patient Eligibility

Confirm patient eligibility by collecting the information listed below:

1. Registering MD's name
2. Patient's race, sex, and DOB
3. Three letters (or two letters and a dash) for the patient's initials
4. Copy of signed consent form
5. Completed eligibility checklist, signed and dated by a member of the study team
6. Copy of appropriate source documentation confirming patient eligibility

4.2 Screen Failures

Screen failures are defined as participants who consent to participate in the clinical trial but are not subsequently entered in the study. A minimal set of screen failure information is required to ensure transparent reporting of screen failure participants, to meet the Consolidated Standards of Reporting Trials (CONSORT) publishing requirements and to

respond to queries from regulatory authorities. Minimal information includes demography, screen failure details, eligibility criteria, and any serious adverse event (if applicable).

5.0 STUDY TREATMENT

5.1 Overview

Patients will be randomly assigned in a double-blind fashion to receive either duvelisib 25mg or placebo twice daily for up to 10 days. Patients who have significant clinical improvement prior to day 10 and are going to be discharged from the hospital may discontinue the treatment early with investigator permission.

Blocks of 10 patients will be used to allocate patients to duvelisib or placebo. Due to differences in color between the duvelisib and placebo capsules, we will employ methods in this trial to maintain the blinding of the investigator to the best of our ability (e.g. having the drug dispensed by alternative personnel). If this study were to lead to a pivotal trial, matched placebos would be manufactured for such a trial.

Treatment is dosed orally and can be administered with or without food. For patients unable to administer orally, a duvelisib suspension will be administered through a nasogastric/orogastric tube. In this event, the capsule(s) will be opened and the dose will be placed in 40mL water and stirred until dissolved. The suspension should be administered using an appropriate syringe within 6 hours after preparation. Following administration, the tube should be rinsed with approximately 75 mL of water.

If a dose is missed by fewer than 6 hours, administer the missed dose right away and take the next dose as usual. If a dose is missed by more than 6 hours, the patient should not take an additional dose, but should take the next usual prescribed dose.

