Study Description:	Patients with a diagnosis of COVID-19 with critical disease manifestations will be randomly assigned to receive duvelisib or placebo
Objectives:	
Primary Objective: To evaluate the efficacy of duvelisib for the treatment of COVID-19 disease manifestations.
 
Secondary Objectives: To evaluate the safety and tolerability of duvelisib for the treatment of COVID-19 disease manifestations.

Endpoints:	
Primary Endpoint:
 
 • 28 day overall survival 
Secondary Endpoints:
 
 • Hospital and ICU length of stay • Duration of ventilator • Duration of vasopressors • Duration on renal replacement therapy • Viral kinetics • Adverse Events
Study Population:	Twenty-eight patients (approximately 14 per arm) over the age of 18 with a diagnosis of COVID-19 with advanced disease manifestations including one or more of the following: extensive lung involvement, respiratory failure, shock, or cardiac dysfunction.
Phase:	Pilot Phase 2
Description of Sites/Facilities Enrolling:	This is a multi-center study open at Washington University School of Medicine and Missouri Baptist Medical Center.
Description of Study Intervention:	Patients will receive either duvelisib 25mg or placebo for 10 days. Both participants and researchers will be blinded.
Study Duration:	18 months
Participant Duration:	6 months

Table of Contents

PROTOCOL SUMMARY	4
1.0 BACKGROUND AND RATIONALE	7
1.1 COVID-19 and Cytokine Release Syndrome	7
1.2 Lessons and Preclinical Data from CART-related CRS	7
1.3 Gene edited CART model for the Mitigation of CRS	8
1.4 PI3K Inhibition Potently Mitigates CRS in Pre-clinical CART Model.....	9
1.5 PI3K Inhibition to Mitigate Pathogenesis of Advanced COVID-19	10
2.0 OBJECTIVES	11
2.1 Primary Objective	11
2.2 Secondary Objectives.....	11
2.3 Objectives and Endpoints Table	11
3.0 PATIENT SELECTION	12
3.1 Inclusion Criteria	12
3.2 Exclusion Criteria	13
3.3 Inclusion of Women and Minorities	13
4.0 REGISTRATION PROCEDURES	13
4.1 Confirmation of Patient Eligibility	13
4.2 Screen Failures.....	13
5.0 STUDY TREATMENT	14
5.1 Overview.....	14
5.2 Dose Modifications.....	14
5.3 Supportive Care	15
5.4 Viral Load Monitoring.....	17
5.5 Worsening COVID-19 Symptomology	17
5.6 Duration of Therapy.....	17
5.7 Duration of Follow-up	18
5.8 Lost to Follow-Up.....	18
6.0 PHARMACEUTICAL INFORMATION.....	18
6.1 Duvelisib.....	18
7.0 SCHEDULE OF ASSESSMENTS.....	20
8.0 CORRELATIVE STUDIES	22

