6.1.2 Dose Forms and Strengths

Duvelisib capsules are for oral administration and are supplied as white to off-white opaque and Swedish orange opaque capsules (25 mg, on anhydrous basis) or pink opaque capsules (15 mg, on anhydrous basis), and contain the following inactive ingredients: colloidal silicon dioxide, crospovidone, magnesium stearate, and microcrystalline cellulose. Capsule shells contain gelatin, titanium dioxide, black ink, and red iron oxide.

Placebos are supplied as matching size white to off-white opaque capsules containing the inactive above.

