12.0 STATISTICAL CONSIDERATIONS

This is a double-blinded randomized pilot phase II study. The purpose of this study is to provide hypothesis generating data on the efficacy and toxicity duvelisib for the treatment of COVID-19. The total accrual goal is 28 patients, approximately 14 in each arm. Blocks of 10 patients will be used to allocate patients to either duvelisib or placebo. The projected enrollment time frame is 3 months (approximately 9 patients per month).

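### A single fixed block size of 10 is disclosed in a protocol whose capsules differ in colour and which describes no concealment of the next assignment: a modest, conditional selection-bias risk that is cheap to reduce

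*Combined protocol and SAP*

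**What the plan says.** Section 5.1 (Overview) states "Blocks of 10 patients will be used to allocate patients to duvelisib or placebo". Section 12.0 (Statistical Considerations) says the same: "Blocks of 10 patients will be used to allocate patients to either duvelisib or placebo". No other block size is named, and the split within a block is not written. Section 12.0 gives the target: "The total accrual goal is 28 patients, approximately 14 in each arm".

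Section 5.1 then acknowledges a limit on the blinding: "Due to differences in color between the duvelisib and placebo capsules", the trial will use methods to "maintain the blinding of the investigator to the best of our ability (e.g. having the drug dispensed by alternative personnel". Section 6.1.2 lets a reader tell the arms apart. Active capsules are "supplied as white to off-white opaque and Swedish orange opaque capsules (25 mg, on anhydrous basis"), whereas "Placebos are supplied as matching size white to off-white opaque capsules". The protocol summary nevertheless says that both participants and researchers will be blinded.

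The registration steps in section 4.1 include no randomization or concealment step. The protocol does not say who generates or holds the list or how the next assignment is hidden. The summary says "This is a multi-center study open at Washington University School of Medicine and Missouri Baptist Medical Center", but nothing states whether the list is separate by site.

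**The concern.** In a permuted block of known length, each assignment that becomes known narrows what is left, and the last ones can become certain. The protocol tells every holder the block length and what each capsule looks like. If those who enrol patients also learned the earlier assignments, they could partly anticipate the next one.

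This is a different problem from blinded outcome assessment, because it affects who enters each arm. There is some room to act on such knowledge: one exclusion criterion in section 3.2 rests on investigator opinion, and screening may take place within 7 days of registration (section 7.0, footnote 1). A prognostic imbalance created at entry would not be removed by the intent-to-treat analysis or Fisher's exact test in section 12.2.

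**Working it through.** **The plan's own figures.** Section 12.1 claims more than 80% power for 20% versus 60% survival, and about 40% power for 40% versus 60%, with 14 per arm at one-sided 0.20. Exact enumeration of the one-sided Fisher test gives 82.7% and 40.1%, so both reproduce. Stopping at 28 leaves the third block incomplete: the final split is 14:14 with probability 56% and 15:13 or 13:15 with probability 44%. Power at 20% versus 60% is then still 83–84%. The power statement is not affected by this point.

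**Inputs for predictability.** Block size 10 (5.1, 12.0); N = 28, so two full blocks plus 8 places of a third (12.0). Assumption: 5:5 within each block.

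**One block, all earlier assignments known.** After k assignments, with x to one arm, the chance of that state is C(5,x)·C(5,k−x)/C(10,k). The best guess is the arm with more places left, right with probability max(5−x, 5−k+x)/(10−k). Averaging over x:

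| Earlier assignments known (k) | Best guess for the next is right | Next is certain |
|---|---|---|
| 0 | 50.0% | 0 |
| 1 or 2 | 55.6% | 0 |
| 3 or 4 | 59.5% | 0 |
| 5 | 64.3% | 0.8% |
| 6 | 64.3% | 4.8% |
| 7 | 72.2% | 16.7% |
| 8 | 72.2% | 44.4% |
| 9 | 100% | 100% |

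- Certain per full block: 2m/(m+1) with m = 5 is 10/6 = 1.67.
- Correct guesses per full block: 5 + (2^10/C(10,5) − 1)/2 = 5 + (1024/252 − 1)/2 = 6.53.

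**Whole trial.** The first 8 places of a block contribute 0.008 + 0.048 + 0.167 = 0.22 certain assignments and 4.81 correct guesses.

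- Certain: 2 × 1.667 + 0.222 = 3.56 of 28 (13%).
- Correct guesses: 2 × 6.532 + 4.810 = 17.87 of 28 (64%).
- With separate lists by site (14/14, 20/8 or 24/4 assumed): 3.3 to 3.6 certain and 62–64% correct.

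**Imperfect knowledge (simulated; accuracy is assumed).** If past assignments are inferred with 90%, 80%, 70% or 60% accuracy, correct guesses are 59%, 56%, 53% and 52%.

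**What steering could do (illustration).** The documents give no size for steering. Suppose the enrolled patient's survival probability is δ higher when duvelisib is expected next and δ lower when placebo is. With guess rate g, the spurious survival difference is 2δ(2g − 1). At δ = 10 points this is 20 × 0.28 = 5.6 points for g = 0.64 and 20 × 0.12 = 2.4 points for g = 0.56.

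**Would varying the block size help?** Simulated for N = 28, with all past assignments known and a guesser who knows the possible sizes but not their order:

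| Scheme | Certain assignments | Correct guesses |
|---|---|---|
| Fixed 10 | 3.6 | 64% |
| 8/10/12 | 0.5 | 64% |
| 6/8/10 | 0.5 | 66% |
| 4/6/8 | 0.6 to 0.7 | 67–68% |
| 4/6 | 1.5 to 1.6 | 69% |

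Varying the size removes most of the certainty but does not lower the overall guess rate, and small blocks raise it.

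**The case against.** A reader might infer that staff who pick up a few assignments can predict later ones and steer enrolment. The documents do not support that, for four reasons.

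- **Knowledge needed.** Two to four known assignments give only a 56–60% guess for the next. Certainty is impossible before five are known, and rare (0.8%) at five. The 64% figure requires every earlier assignment to be known.
- **The chain is not shown.** Someone must recognise capsules, the knowledge must reach those who enrol, a near-complete tally must be kept (possibly across two sites), and someone must act on it. Section 5.1 plans dispensing by other personnel precisely to shield the investigator. Patients who cannot take capsules receive a suspension from opened ones, so the shell need not be visible when it is given.
- **Limited discretion.** Most eligibility criteria are laboratory, imaging or support thresholds. Critical illness limits deferral, and section 4.2 requires screen failures after consent to be recorded.
- **Purpose.** This is a hypothesis-generating pilot. Section 12.1 says confirmatory studies would be needed, and section 5.1 foresees matched placebos for a pivotal trial. Ten is also already a fairly large block for 28 patients.

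These arguments stand as limits on the size and likelihood of the problem. They do not remove it. The safeguard is best-effort, names only the investigator, and does not mention bedside staff or patients. The documents neither show nor rule out that enrolling staff learn past assignments, and they describe no concealment of the next one.

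**Conclusion.** The point holds as a modest, conditional risk. A constant block size is disclosed twice, the capsules can be told apart by colour, and concealment of the next assignment is not described. In the worst case, with every earlier assignment known and a 5:5 split, about 3.6 of 28 assignments are certain and 64% are guessable; at 80% accuracy of inference it is about 56%. Actual bias would also need someone to act on the guess, and its size depends on a steering effect that the documents do not give. It would be wrong to conclude that allocation is predictable in practice or that steering is expected. It would be equally wrong to think that mixed block sizes alone solve the problem while capsules are distinguishable. This is a worthwhile low-cost improvement, not a flaw that invalidates the design.

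**What to change.** 1. Delete the block size from sections 5.1 and 12.0. Say instead that allocation details are in a restricted randomization file, held by the unblinded dispensing pharmacist and a statistician outside the enrolling team.
2. Vary the block size at random around 10, for example 8, 10 and 12, and avoid smaller blocks. Certain assignments fall from about 3.6 to about 0.5; the guess rate stays at about 64%.
3. Because step 2 does not address the visible colour difference, state that those who enrol patients will see neither capsules nor the list. Describe how the next assignment is released after registration, and say whether lists are separate by site.

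The cost is a new list, short text edits and some separation of staff roles. The downside is that the first 10 patients (the correlative set, section 8.0) and the DSMB reports tied to 10 and 20 enrolments (section 11.0) may not be exactly balanced. With 8/10/12 equally likely, the chance of an exact 5:5 split at patient 10 is the average of three cases. A first block of 8 gives (4/7 + 5/9 + 6/11)/3 = 0.56, a first block of 10 gives 1, and a first block of 12 gives 6/11 = 0.55. The average is about 70%; otherwise the split is 6:4.

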5.2 Dose Modifications

Participants will be evaluated for toxicity according to the Common Terminology Criteria for Adverse Events (CTCAE) of the National Cancer Institute (NCI) version 5.0. Dose modifications for treatment-emergent adverse events are listed in the table below. If the dose is reduced for toxicity, escalation may occur at the discretion of the treating physician following resolution/stabilization of the toxicity.

Treatment-Emergent Adverse Event	Management for Duvelisib/Placebo
Neutropenia	
Grade \leq 3	No change.
Grade 4	Hold treatment until \leq Grade 2. When resumed, reduce treatment by one dose level.
Thrombocytopenia	
Grade \leq 3	No change.

Grade 4	Hold treatment until \leq Grade 3. When resumed, reduce treatment by one dose level.
Anemia	
Any	Dose delay is not required for anemia, unless deemed necessary by the treating physician. Transfusions and/or erythrocyte stimulating agents are allowable.
Pneumonitis	
Grade 1	No change.
Grade 2	If suspected related to treatment, treat with systemic steroid therapy and hold treatment until \leq Grade 1 OR patient returns to baseline (where patient had a predetermined abnormal baseline). When resumed, reduce treatment by one dose level. If unrelated to treatment, no change unless deemed necessary by the treating physician.
Grade \geq 3	Discontinue.
Viral Load Elevation	
Increase in viral load of >0.5 log on two consecutive days, or >1 log increase in one day	See section 5.4. If viral load elevation is suspected to be related to treatment, hold treatment until patient returns to baseline (where patient had a predetermined abnormal baseline). Permission required from the principal investigator prior to re-treatment. If resumed, reduce treatment by one dose level.
All other events	
Grade \leq 2	No change.
Grade 3	If suspected related to treatment, hold treatment until \leq Grade 1 OR patient returns to baseline (where patient had a predetermined abnormal baseline). When resumed, reduce treatment by one dose level. When resumed, reduce treatment by one dose level. If unrelated to treatment, no change unless deemed necessary by the treating physician.
Grade 4	For Grade 4 lab abnormalities: Hold treatment until \leq Grade 1 OR patient returns to baseline (where patient had a predetermined abnormal baseline). Permission required for the principal investigator prior to re-treatment. For Grade 4 treatment-related adverse events with clinical manifestation (eg. life-threatening colitis, cutaneous reactions, infections): Discontinue study treatment

5.2.1 Duvelisib/Placebo Dose Levels

1	25 mg twice daily
-1	15 mg twice daily
-2	Discontinue

5.3 Supportive Care

Patients should receive full supportive care, including but not limited to intravenous fluids, transfusions of blood and blood products, antibiotics, antivirals, antibacterial agents, and antiemetics, when appropriate at the discretion of the treating clinician.

5.3.1 Recommended Prophylaxis Medications

Patients should receive prophylaxis for *Pneumocystis jirovecii* (PJP) during study treatment. Following completion of study treatment, continue PJP prophylaxis until the absolute CD4+ T cell count is greater than 200 cells/ μ L.

CMV prophylaxis may be considered in patients deemed high risk per institutional guidelines, although is not mandatory. CMV viral load monitoring will occur for seropositive patients.

5.3.2 Prohibited/Discouraged Medications

Strong CYP3A inducers should be avoided as they decrease duvelisib area under the curve (AUC) which may reduce duvelisib efficacy.

Strong CYP3A inhibitors should be avoided as they increase duvelisib AUC which may increase the risk of duvelisib toxicities. If strong CYP3A inhibitors are clinically necessary, the dose of duvelisib should be reduced to 15 mg BID.

Other drugs that are sensitive CYP3A4 substrates should be avoided as administration of duvelisib increases AUC of these drugs which may increase the risk of toxicities. If sensitive CYP3A4 substrates are clinically necessary, it is recommended to reduce the dose of the sensitive CYP3A4 substrate and monitor for signs of toxicities.

5.3.3 Standard of Care Therapy

The standard of care for patients with severe or critical COVID-19 continues to evolve and may be defined differently due to local practice habits and the availability or shortage of therapies.

Ventilatory strategies and management of critical illness should proceed according to institutional standards, as should the use of remdesivir.

Patients who are not already receiving a corticosteroid should be started on a dose of at least dexamethasone 6mg daily oral or intravenously at the time of screening (Day -1) and continue through Day +10 or beyond, unless contraindicated, per results of the RECOVERY Trial.[19]

5.3.4 Investigational or Off-Label Treatments for COVID-19

Patients who have received other investigational or off-label agents previously are eligible for study and these agent(s) may be continued at the discretion of the treating physician.

During study treatment, screening through Day 10, the addition of investigational or off-label agents for patients on the study is discouraged. However, physicians who believe use of such agents is warranted should discuss with the principal investigator. If such agents are administered, patients are permitted to continue on duvelisib.

5.4 Viral Load Monitoring

All patients will have three consecutive days of viral load monitoring prior to receiving duvelisib, on Screening day, Day -1, and Day 1 (see Section 7.0), to establish the baseline viral load and trend. For patients with an increase in viral load of >0.5 log on two consecutive days, or >1 log increase in one day, clinical judgement should be used to determine if any continued rising viral load is suspected to be related to study treatment. If suspected to be related to study treatment, follow dose modifications as outlined in section 5.2. If thought to be unrelated to study treatment, i.e. keeping with baseline trend, no change unless deemed necessary by the treating physician.

5.5 Worsening COVID-19 Symptomology

Patients with clinically worsening symptoms of COVID-19 may be removed from study treatment at any time per discretion of the treating physician and additional treatments may be commenced. However, patients should continue to be followed as per the protocol calendar in section 7.0.

5.6 Duration of Therapy

If at any time the constraints of this protocol are considered to be detrimental to the patient's health and/or the patient/surrogate no longer wishes continuation of the protocol therapy, the protocol therapy should be discontinued and the reason(s) documented in the case report forms.

Patients will be removed from the study for any of the following reasons:

- Death
- Adverse event(s) that, in the judgment of the investigator, may cause severe or permanent harm or which rule out continuation of the study drug
- General or specific changes in the patient's condition that render the patient unacceptable for further treatment in the judgment of the investigator
- Suspected pregnancy
- Serious noncompliance with the study protocol

- Lost to follow-up
- Patient/surrogate withdraws consent
- Investigator removes the patient from study
- Investigator decides to close the study

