5.7 Duration of Follow-up

All patients will be followed as according to the protocol calendar in Section 7.0 for the duration unless the patient withdraws consent or is lost-to-follow-up. Following the safety follow-up visit, patients will continued to be monitored for survival and late-onset toxicity every 3 months for up to 6 months. For these long-term follow-up visits, a telephone visit can be made in lieu of a physical visit.

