10.0 REGULATORY AND REPORTING REQUIREMENTS

The entities providing oversight of safety and compliance with the protocol require reporting as outlined below. Please refer to Appendix C for definitions and Appendix D for a grid of reporting timelines.

Adverse events will be tracked from start of treatment through Day 29. All adverse events must be recorded on the toxicity tracking case report form (CRF) with the exception of:

- Baseline adverse events, which shall be recorded on the medical history CRF

Refer to the data submission schedule in Section 9 for instructions on the collection of AEs in the EDC.

Reporting requirements for Washington University study team may be found in Section 10.1. Reporting requirements for secondary site study teams participating in Washington University-coordinated research may be found in Section 10.2.

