10.1.2 Reporting to Verastem

All initial and follow-up SAEs to include unanticipated problems and pregnancies, must be reported to Verastem, Inc. Safety and Pharmacovigilance via PPD at [contact] within 24 hours of knowledge of the event concerning the Verastem, Inc. product. Reports should be submitted in English via the sponsor-investigator internal SAE/pregnancy forms, MedWatch or CIOMS forms.

Pregnancy per se is not considered an AE unless there is cause to believe that the study interventions may have interfered with the effectiveness of a contraceptive medication or if the outcome of the pregnancy meets SAE criteria (miscarriage or congenital anomaly/birth defect, etc.), in which case it should be reported in the same manner and timelines as an SAE. In addition, any infant death or congenital anomaly occurring after 30 days that the Investigator suspects is related to the in-utero exposure to the study interventions should also be reported as an SAE. Hospitalization for normal delivery of a healthy newborn is not an SAE.

Since duvelisib has not been evaluated in pregnant or nursing women, the treatment of pregnant women or WCBP who are not using highly effective contraception is contraindicated.

Pregnancies occurring in subjects or partners of male subjects during the study intervention period and until 30 days after the subject's last dose of study interventions are considered immediately reportable events. If a pregnancy occurs in a subject, study interventions must be discontinued immediately. The pregnant woman should be referred to an obstetrician/gynecologist experienced in reproductive toxicity for further evaluation and counseling. The Investigator will observe the pregnant woman until completion of the pregnancy and must notify Verastem of the outcome within 24 hours of the Investigator's knowledge of the pregnancy outcome using a Pregnancy Outcome Form. This notification includes pregnancies resulting in live, "normal" births.

SAE reports must contain the following minimum information:

- At least one identifiable reporter
- One single identifiable patient
- At least one suspect adverse reaction
- At least one suspect medicinal product
- The sponsor-investigator's assessment of causality for the event

All such occurrences listed in this section shall be reported to Verastem using an approved local regulatory form and/or SAE form provided by Verastem and sent by facsimile or email to the following:

[contact]

Email: [contact]

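### Section 5.6 removes patients from the study for reasons that only stop treatment, contradicting 5.5 and 5.7, and 12.2 is ambiguous on how removed or consent-withdrawn patients count at Day 28

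*Combined protocol and SAP*

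**What the plan says.** - **Section 5.6 (Duration of Therapy).** The opening paragraph concerns stopping protocol therapy. The list that follows is introduced with "Patients will be removed from the study for any of the following reasons" and has nine entries. One is an adverse event that may cause severe or permanent harm or "which rule out continuation of the study drug". Another is a change in condition that makes the patient unacceptable for further treatment.
- **Section 5.7.** All patients are followed on the protocol calendar "unless the patient withdraws consent or is lost-to-follow-up". Survival contacts then continue every 3 months for up to 6 months, and these may be by telephone.
- **Section 5.5.** Patients taken off treatment for worsening COVID-19 stay in follow-up: "patients should continue to be followed as per the protocol calendar in section 7.0".
- **Section 5.8.** Loss to follow-up is defined narrowly, as three missed scheduled visits in a patient who cannot be contacted.
- **Section 10.0.** "Adverse events will be tracked from start of treatment through Day 29".
- **Section 12.2.** The primary analysis of 28-day survival is intent-to-treat in all randomized patients. It assumes at least 28 days of follow-up for everyone. Patients lost to follow-up before then, from whatever cause, are treated as deaths. Investigator removal and withdrawal of consent are not named.

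**The concern.** A site that applies 5.6 literally would end study participation when an adverse event or a change in condition ends treatment. Day 28 vital status could then go uncollected in a living randomized patient. Adverse event tracking to Day 29 could also stop early in the patients removed because of an adverse event, although safety is the secondary objective.

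The analysis section does not settle how such a patient counts. Read with the definition in 5.8, and with 5.6 listing loss to follow-up separately from consent withdrawal and investigator removal, the failure rule in 12.2 may not reach removed or withdrawn patients. Read broadly, it may turn a living patient into a death. With about 14 patients per arm, one such decision is visible in the result.

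**Working it through.** **1. Counting the reasons in 5.6.** Nine are listed. Two match the exceptions in 5.7 (consent withdrawal, loss to follow-up): 9 − 2 = 7. Setting aside death leaves 6. Setting aside closure of the whole study, which is not a patient-level reason, leaves 5: adverse event, unacceptable for further treatment, suspected pregnancy, serious noncompliance, and removal by the investigator. The first two are worded in terms of the drug or treatment.

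**2. The passages side by side.** Take a patient whose worsening disease makes further treatment unacceptable. Under 5.5 the patient stops treatment and stays on the calendar. Under 5.7 the patient is followed, since neither exception applies. Under 5.6 the patient is removed from the study. These cannot all be followed.

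**3. The plan's own power.** Inputs from 12.1 and 12.2: 14 per arm, 28-day survival 20% (placebo) vs 60% (duvelisib), one-sided type I error 0.20, Fisher's exact test. I took the test as one-sided at 0.20.

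Power = Σ over t, c of Bin(t; 14, pT) × Bin(c; 14, pC) × 1[one-sided Fisher p(t, c) ≤ 0.20]

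- 20% vs 60%: 82.7% (12.1 states more than 80%)
- 40% vs 60%: 40.1% (12.1 states about 40%)

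Both stated figures reproduce.

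**4. Effect of scoring living patients as deaths.** The rates below are assumptions.

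- One patient: 1/14 = 7.1 points of an arm's 28-day survival.
- A share m of survivors misscored in both arms replaces each survival p by p(1 − m):

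| m | Placebo | Duvelisib | Power |
|---|---|---|---|
| 0 | 0.20 | 0.60 | 82.7% |
| 5% | 0.20 × 0.95 = 0.19 | 0.60 × 0.95 = 0.57 | 80.2% |
| 10% | 0.20 × 0.90 = 0.18 | 0.60 × 0.90 = 0.54 | 77.8% |

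- Exactly one duvelisib survivor misscored (of 14 × 0.60 = 8.4 expected), none on placebo: the rejection rule is applied to (t − 1, c), and power is 71.6%, a loss of 82.7 − 71.6 = 11.1 points.
- One patient can move a result across 0.20: 8/14 vs 4/14 alive gives one-sided p = 0.126, and 7/14 vs 4/14 gives p = 0.220.

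**5. False positives.** With true survival equal in both arms and 20% of placebo survivors only misscored, the one-sided rejection rate is 6.8%, 15.8%, 19.1% and 19.7% at survival of 10%, 20%, 30% and 40%. It stays below the nominal 20% across the 10–40% range that 12.1 cites.

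**The case against.** The best defence is that this is loose wording with a workable rule around it. Section 5.6 is headed and introduced as being about therapy, follow-up has its own section with two clear exceptions, and 5.5 points the same way. Section 9.0 already calls for a 28-day survival form, and telephone follow-up is allowed. A site that reads 5.5 to 5.7 together and completes the form would lose little. The trial is also a hypothesis-generating pilot. All of this stands and keeps the point minor. It does not remove the literal contradiction between 5.6 and 5.7.

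Stronger readings that a reader might infer are not supported:

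- **That 12.2 is silent, or that removed patients may be dropped.** Every randomized patient is included, and the failure rule for loss to follow-up can naturally be read to cover removals and withdrawals. The problem is ambiguity.
- **That 12.2 requires a patient known to be alive at Day 28 to be scored as a death.** Nothing says so. It is one possible outcome of a broad reading.
- **That 5.2 and 10.1.2 also contradict 5.6.** For Grade 4 treatment-related clinical events 5.2 says "Discontinue study treatment" and does not mention follow-up. For pregnancy, 10.1.2 says "If a pregnancy occurs in a subject, study interventions must be discontinued immediately" and "The Investigator will observe the pregnant woman until completion of the pregnancy". That is a duty to observe the pregnancy, which is compatible with leaving the trial.
- **That the trial is materially biased or its power wrong.** The larger shifts need misscoring in one arm only, for which the documents give no basis, and the stated power is correct.

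**Conclusion.** The concern holds as a minor inconsistency in the protocol with an ambiguity in the analysis rule. Section 5.6 cannot be followed together with 5.5 and 5.7, and it works against adverse event tracking through Day 29 and the assumption in 12.2 of 28-day follow-up for all. Whether removed or consent-withdrawn patients fall under the failure rule in 12.2 depends on how it is read.

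The figures show sensitivity and are not a forecast. They assume that living patients are scored as deaths, at rates the documents do not give. On that basis the loss of power is 2.5 points (82.7 − 80.2) or 4.9 points (82.7 − 77.8) when 5% or 10% of survivors in both arms are affected. The 11.1-point loss applies only if exactly one duvelisib survivor, and no placebo survivor, is misscored. Treating truly unknown status as failure is an acceptable prespecified convention and is not criticised here.

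**What to change.** **Protocol.** Reconcile 5.6 with 5.5 and 5.7 so that ending study treatment, or removal by the investigator, does not end Day 28 survival follow-up or adverse event tracking. This takes no position on when treatment should stop.

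**Section 12.2.** State that:

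1. Day 28 vital status is obtained for every randomized patient unless consent to this is withdrawn, using the chart, telephone or the planned 3- and 6-month contacts.
2. A patient known to be alive at Day 28 counts as a survivor, whether or not removed from treatment or study.
3. Apart from known deaths, only patients whose Day 28 status remains unknown after these steps, including after withdrawal of consent, count as deaths, whether or not they meet the definition in 5.8.

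**Cost.** Wording only. The Day 28 survival form, telephone visits and later survival contacts are already planned, and the sample size does not change.
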